### **4.3 Obtaining, Handling, Storage, Shipment of Specimens**

Whole blood (up to 15 ml for visit 1 and 5ml for visits 2 and 3) will be collected by venipuncture. Specimens will be labelled with the participant’s study number and the date the sample was drawn. Samples will be processed on-site for complete blood cell count and differential, quantitative IgG, IgA and IgM levels and T and B lymphocyte subsets.

#### 4.3.1 Immunologic assessment

##### *Quantitative immunoglobulins*

Up to 5 ml of whole blood will be collected for baseline quantitative measurement of total IgA, IgG and IgM levels. Samples will be processed at the local clinical laboratory according to standard procedures and denominated results will be transferred to the coordinating centre. At some centres this testing is conducted as part of routine clinical care.

##### *Lymphocyte subsets*

Up to 5 ml of whole blood will be collected for baseline quantitative measurement of T, B and NK lymphocyte subsets. Samples will be processed for flow cytometry at the local laboratory according to standard procedures and denominated results will be transferred to the coordinating centre.

#### 4.3.2 Serologic testing

Up to 5 mL of whole blood will be collected in a serum separator tube by venipuncture. After collection, blood will be kept at room temperature for 30 minutes to clot. Blood will then be centrifuged for 10 minutes at approximately 2500 RPM. Serum will be separated, aliquoted and frozen at -20°C in the local clinical or research laboratory.

Samples will be batch shipped on dry ice to the Canadian Center for Vaccinology's research laboratory at the IWK Health Centre in Halifax, NS approximately every 3-6 months where they will be stored at -80°C until they are processed locally and/or shipped to other laboratories as below.

Tetanus, pertussis toxoid and varicella IgG measurement will be conducted at the Canadian Center for Vaccinology laboratory using validated enzyme immunoassays.

Pneumococcal serotype-specific IgG levels to vaccine serotypes will be measured at McGill University Health Centre.

### **4.4 Modifying/Discontinuing Planned Vaccination/Treatment**

#### 4.4.1 Temporary Contraindications

Prior to immunization, possible contraindications to vaccination will be reviewed. If temporary contraindications are present, vaccination will be postponed and re-attempted within the allowable time frame for enrolment (up to 12 months post-chemotherapy).

Temporary contraindications to vaccination are as follows:

- An acute illness with or without fever (temperature > 38.0°C).

#### 4.4.2 Definite Contraindications

Subject has a known hypersensitivity to any component of the vaccine.

### **4.5 Clinical Supplies**

As per policies at each study site. Where additional supplies are needed above what is considered routine clinical care, the costs will be covered in the study budget.

### **4.6 Products**

Only licensed vaccines will be administered to participants including: PCV13 (Prevnar®13, Pfizer Canada, Inc.), PPV23 (Pneumovax® 23, Merck Canada Inc., or Pneumo 23®, sanofi pasteur Ltd.) and DTaP-IPV-Hib (Pediacel®, sanofi pasteur Ltd, or Infanrix®-IPV/Hib, GlaxoSmithKline Inc.).

#### 4.6.1 PCV13

This vaccine will be administered according to NACI guidelines for children at high risk of IPD, with the exception that all participants will receive a dose of PCV13, regardless of whether they

have previously received a dose of PCV13 after 12 months of age and prior to initiation of chemotherapy. This practice is already conducted routinely at four Canadian pediatric oncology sites, based on our recent survey. However, as per NACI guidelines, if a participant received PPV23 within 12 months of enrolment, they will not be eligible to receive PCV13.

#### 4.6.2 PPV23

This vaccine will be administered according to NACI guidelines for children at high risk of IPD. Children who have previously received PPV23 will not be reimmunized.

#### 4.6.3 DTaP-IPV-Hib

This formulation of diphtheria-tetanus-pertussis vaccine is licensed for children up to 7 years of age due to the increased risk of local reactions in older children and adolescents from the higher doses of diphtheria toxoid and acellular pertussis antigens. Administration of this vaccine to all participants regardless of age would be in keeping with current guidelines in the UK and Australia for patients who have completed chemotherapy for ALL. Additionally, based on our survey, the majority of pediatric centres administer DTaP-IPV-Hib to all bone marrow transplant recipients regardless of age due to evidence of improved vaccine responses in this population, in keeping with current IDSA guidelines.[4] The administration of the Hib component is consistent with NACI guidelines for patients with hematologic malignancies.

If DTaP-IPV-Hib is not available, DTaP-IPV plus Hib vaccine may be given.

### **5. Surveillance, Monitoring and Assessment**

#### **5.1 Immunologic Status**

Immunologic status will be assessed by quantitative measurement of total IgA, IgG and IgM and by assessment of T, B and NK lymphocyte subsets, as available at the local laboratory. At a minimum the following will be assessed on all patients:

- total white blood cell count, total lymphocyte count, total and percentages of: total T cells (CD3+), CD4+ T cells, CD8+ T cells, CD4/CD8 ratio, B cells (CD19+), and NK cells (CD56+/CD16+).

Where available, in addition to the above, an expanded panel of cell surface markers will be measured to determine total and percentages of the following subpopulations:

- memory T cells (CD3+/CD4+/CD45RO+)
- naïve T cells (CD3+/CD4+/CD45RA+)
- regulatory T cells (CD3+/CD4+/CD25+)
- activated T cells (CD3+/CD4+/HLA-DR+)
- memory B cells (CD19+/CD27+)
- unswitched B cells (CD19+/sIgD+)

#### **5.2 Immune Responses to Vaccines**

Vaccine antigens to be tested include tetanus, pertussis toxoid, varicella and 14 pneumococcal vaccine serotypes (1, 3, 4, 5, 6B, 7F, 8, 9V, 9N, 12F, 14, 18C, 19F, 23F). Of the pneumococcal

serotypes tested, 10 are included in both PCV13 and PPV23 (1, 3, 4, 6B, 7F, 9V, 18C, 19F, 23F) and 3 are only included in PPV23 (8, 9N, 12F). Vaccine responses will be determined by measurement of GMT to vaccine antigens pre-vaccination, 2 months and 12-15 months post-vaccination, and calculating GMT ratios. An adequate vaccine response will be defined as GMT ratio  $\geq 4$  (post-vaccination/pre-vaccination). For pneumococcal serotypes, GMT  $\geq 0.35$   $\mu\text{g}/\text{ml}$  is the World Health Organization accepted correlate of protection in clinical trials,[31] while GMT  $\geq 0.50$   $\mu\text{g}/\text{ml}$  has been used in other studies of immunocompromised children.[27, 41] The proportion of participants with GMT at or above these thresholds at baseline, at 2 months post-PCV13, and at 12-15 months post-PCV13+PPV23 immunization will be reported for each serotype. Vaccine titres will also be reported as “seropositive” or “seronegative” for tetanus and varicella.

## 5.3 Adverse Events

### 5.3.1 Definitions

*Adverse event following immunization (AEFI):* Any untoward medical occurrence in a patient that is temporally associated with vaccination and not clearly attributable to another known cause [42].

*Serious adverse event (SAE):* The Public Health Agency of Canada defines a serious adverse event following immunization as any untoward medical occurrence that:

- Requires in-patient hospitalization or prolongation of existing hospitalization for  $>24$  hours
- Results in permanent disability
- Is a congenital anomaly or birth defect
- Is fatal

*High impact AEFI:* event that results in hospitalization for 24hrs or less or medical supervision out of hospital or requires  $\geq 3$  physician assessments for AEFI and/or leads to disability  $>3$  days (unable to perform daily activities, unable to go to work, unable to attend school).

*Moderate impact AEFI:* event that requires an unscheduled physician visit, including emergency department visit or new or change in medication or leads to 1-3 days of disability.

*Low impact AEFI:* event managed by immunization clinic staff, with telephone advice or during previously scheduled appointment, and/or resulting in  $<24$  hours of disability.

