### **5.3.3 Reporting of Serious Adverse Events**

AEFI will be reported to public health authorities according to provincial and national guidelines. All SAEs will be reviewed by the principal investigator and discussed with co-investigators in a timely manner, as appropriate. AEFI will be reported to public health as per local guidelines. There will be no external safety monitoring board as all vaccines are currently approved for use in this population and will be provided per standard of care.

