## **7. Ethical Considerations**

This research protocol will be submitted to the Research Ethics Board (REB) at each participating site for ethical approval, along with all other necessary documents. At each site, the study will be initiated once approval from the local REB has been received.

This study will be conducted in accordance with the latest version of the Declaration of Helsinki, ICH Good Clinical Practice regulatory guidelines, and requirements regarding ethical committee review, and other statutes and regulations regarding the protection of the rights and welfare of subjects participating in the study.

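### The SAE list in 5.3.1 has no life-threatening criterion, so a life-threatening reaction that resolves within 24 hours is not an SAE, bypasses the principal-investigator review and may be graded differently by different sites

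*Combined protocol and SAP*

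**What the plan says.** Section 5.3.1 gives four SAE criteria:

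- "Requires in-patient hospitalization or prolongation of existing hospitalization for" more than 24 hours
- "Results in permanent disability"
- "Is a congenital anomaly or birth defect"
- death

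Below these sit three impact tiers.

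- **High** is an "event that results in hospitalization for 24hrs or less or medical supervision out of hospital or requires" three or more physician assessments, and/or more than three days of disability.
- **Moderate** is an "event that requires an unscheduled physician visit, including emergency department visit or new or change in medication or leads to 1-3 days of disability".
- **Low** covers events handled by clinic staff, by telephone or at an already scheduled appointment, and/or less than a day of disability.

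The review routes differ by category. Under 5.3.3, "All SAEs will be reviewed by the principal investigator and discussed with co-investigators in a timely manner", with the qualifier that this is done as appropriate. The same section says that there is no external safety board. Under 5.3.2, the site investigator reviews medically attended AEFI and assesses causality. Section 3.1 requires a formal causality assessment from moderate impact upwards. Section 5.3.3 also sends AEFI, not only SAEs, to public health authorities.

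The primary safety outcome (6.3.1) is the frequency of AEFI of moderate impact or greater. Section 6.4 reports three groups: low, moderate, and high impact or serious combined.

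**The concern.** Section 3.1 points to 5.3 for the classification of AEFI severity, but 5.3 grades only the care an event consumed and the days of disability it caused. A reaction can threaten life and still be short and fully reversible. Acute allergic reactions to vaccines are the obvious example. Such an event meets none of the four SAE criteria.

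Two things are at stake.

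- **Oversight.** Review by the principal investigator and co-investigators is the only prompt cross-site look at safety that the protocol describes, and SAEs alone trigger it. Section 6.2 expects 75–80 children and 3.1 names 10 centres, so an average site sees about eight and cannot judge a pattern by itself.
- **Reporting.** A life-threatening reaction graded moderate would share a category with an unscheduled visit for a minor complaint and would be missing from the high-impact-or-serious frequency. Section 1.5 says the results are meant to support immunization recommendations, and 1.4 says that more data on severity are needed in these children.

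**Working it through.** **Step 1: the plan's own safety figure.** Section 6.2 uses 75 vaccinees and the chance of at least one event, 1 − (1 − p)^75.

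- p = 2%: 1 − 0.98^75 = 0.780 (stated 0.78)
- p = 1%: 1 − 0.99^75 = 0.529 (stated 0.53)

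Both reproduce. They depend only on p and n, so adding an SAE criterion does not change them.

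**Step 2: apply the definitions.** Take a life-threatening reaction and vary only its course.

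| Course | SAE criterion met (5.3.1) | Tier whose words fit | Principal-investigator review (5.3.3) | In high-or-serious group (6.4) |
|---|---|---|---|---|
| Treated in the emergency department, home the same day | None | Moderate (emergency visit, new medication), or high if observation counts as out-of-hospital medical supervision | Not triggered | Only if graded high |
| Hospital stay of 24 hours or less | None | High; moderate wording is also met if the child came through the emergency department | Not triggered | If graded high |
| Stay of more than 24 hours | Hospital stay | SAE | Triggered | Yes |
| Permanent disability or death | Yes | SAE | Triggered | Yes |

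The first two rows show the gap. The reaction itself can be equally dangerous in rows one to three; what separates them is how long the child stayed in hospital.

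**Step 3: overlap.** In the first row two tiers fit the same facts. Section 5.3.1 has no rule for an event that meets more than one tier, so two sites can grade the same event differently while both follow the protocol.

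**Step 4: can another route supply a prompt cross-site review?** Site review (5.3.2) is local. There is no external board (5.3.3) and no external monitoring agency (7.5). Case report forms do reach the coordinating centre (8.1.1), and the principal investigator is responsible for the analysis (6.1). However, no timely review of non-serious events is promised, and 4.1 starts data analysis in December 2017, after patient enrolment is due to end in August 2017.

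**Step 5: how often.** The documents give no frequency for life-threatening AEFI. Purely as an assumption, take a per-child frequency of 0.01% to 0.1%.

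- p = 0.1%: 1 − 0.999^75 = 0.072
- p = 0.01%: 1 − 0.9999^75 = 0.0075

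On that range, the chance that the study meets even one such event is below 1 in 10.

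**The case against.** Most of the safety system still works for these events. Site review, formal causality assessment and reporting to public health all apply from moderate impact upwards, and the event enters the primary safety count whether it is graded moderate or high. Section 5.3.2 also provides for a case-by-case decision on reimmunizing the affected child. The vaccines are licensed products and the sample is small. The protocol attributes its SAE list to the national public health agency. All of this stands. It limits the point to classification and to prompt cross-site review.

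Several stronger readings are tempting but not supported.

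- **That anaphylaxis treated in an emergency department must be moderate, or that every such event is misgraded.** High impact includes medical supervision out of hospital, repeated physician assessments and longer disability, so some of these events would already fall in the high-or-serious group. The fair description is that the grade is ambiguous.
- **That the whole scale ranks by length of stay.** Stay separates an SAE from high impact. The lower tiers use physician visits, medication, disability days and who managed the event.
- **That such an event would drop out of the primary safety outcome.** A reaction treated on the spot by clinic staff does fit some of the low-tier wording, but new medication meets the moderate definition. The documents leave this open and do not establish the loss.
- **That the chance of meeting such an event is 0.53 to 0.78.** Those figures are for events at 1% and 2%, and nothing in the documents gives life-threatening reactions those rates.
- **That the list breaches the "ICH Good Clinical Practice regulatory guidelines" cited in section 7.** Neither that guideline's definition nor the national agency's is reproduced, so compliance cannot be judged here.
- **That other participants' vaccination would be affected.** Section 5.3.3 attaches no action to the principal-investigator review, so this harm is inferred.

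**Conclusion.** The point holds as a gap in classification and review. As written, a life-threatening reaction that resolves without a stay of more than 24 hours, permanent disability or death is not an SAE and does not trigger the review in 5.3.3. That is true whether it is graded moderate or high. If graded moderate, it is also absent from the high-impact-or-serious frequency in 6.4, which could then read zero although such a reaction had occurred.

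No estimate, power figure or sample size changes. Few or none of these events are expected in about 75 children, so the case for acting rests on the weight of a single event and the very low cost of the correction. The conclusion rests on the protocol text alone: four SAE criteria, no highest-tier rule, and central review tied to SAEs. It needs no assumption about event rates. The amendment should be made.

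**What to change.** Four short changes:

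1. In 5.3.1, add to the SAE list: *is life-threatening, whatever the length of hospital stay*.
2. In 5.3.3, make clear that these events follow the SAE route, including review by the principal investigator.
3. In 6.4, count them in the high-impact-or-serious group.
4. In 5.3.1, state that an event meeting the words of several tiers takes the highest one.

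The AEFI form needs a matching tick box. Vaccines, visits, sample size and the definition of the primary safety outcome are untouched. The downside is possibly an occasional extra SAE report.

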### 5.3.2 Adverse Event Monitoring

A study nurse will contact caregivers by telephone on days 8-10 and 30-33 post-immunization to elicit local and systemic symptoms and their severity using a standard questionnaire. Patients with AEFI requiring medical attention will be reviewed by the site investigator according to SIC network protocols, including a causality assessment using a published algorithm.[40]

Decisions regarding reimmunization of patients who experience AEFI will be made by the SIC investigator in consultation with the oncologist, patient and their family.

### **5.3.3 Reporting of Serious Adverse Events**

AEFI will be reported to public health authorities according to provincial and national guidelines. All SAEs will be reviewed by the principal investigator and discussed with co-investigators in a timely manner, as appropriate. AEFI will be reported to public health as per local guidelines. There will be no external safety monitoring board as all vaccines are currently approved for use in this population and will be provided per standard of care.

## **6. Data Management and analysis**

### **6.1 Responsibility for the analysis**

The Principal Investigator will take primary responsibility for the analysis. The analysis will be conducted by data analysts at the Canadian Center for Vaccinology (CCfV), IWK Health Centre.

### **6.2 Sample size and Power**

Approximately 278 new cases of ALL are diagnosed annually in Canadian children <15 years of age.[1] We estimate that approximately 50-60% of children diagnosed with ALL will complete chemotherapy, and consent to participate in the study. We expect to recruit 75–80 children over the enrollment period. To ensure adequate power (>75%) to assess differences in vaccine responses according to treatment protocol, at least 30 subjects will be recruited from centres using DCFI protocols, with the remainder recruited from COG centres. Seventy-five age-matched control subjects will be recruited. If at least 60% of controls have protective antibody titres, a sample of at least 75 cases will give 77% power to detect a  $\geq 20\%$  absolute difference in the proportion of cases achieving seroprotection. This sample size will also give 90% power to detect a standardized difference in mean log titre of  $\geq 0.53$  between cases and controls.

*Safety assessment:* With a total sample size of 75 vaccinees, the probability of detecting at least one occurrence of an AEFI that occurs at a frequency of  $\geq 2\%$  in the population is 0.78 and the probability of detecting an AEFI that occurs at a frequency of  $\geq 1\%$  in the population is 0.53.

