#### 1.1.1 Chemotherapy regimens and their immunosuppressive effects

At diagnosis, children are stratified as standard, high or very high risk, depending on clinical and genetic features. The clinical features that predict high risk ALL are: male sex, age <1 year or ≥10 years at diagnosis, presenting peripheral white blood cell (WBC) count ≥50 x10^9/l.

Treatment consists of multiple phases of multi-drug systemic and intrathecal chemotherapy: induction, consolidation, interim maintenance, delayed intensification and maintenance therapy. Total treatment course is approximately 2 years for girls and 3 years for boys. Most pediatric oncology centres in Canada use the treatment protocols developed by the Children's Oncology Group (COG). Three centres use the protocols developed by the Dana-Farber Cancer Institute (DFCI) ALL Consortium.[2] Examples of standard and high risk COG and DFCI ALL protocols are shown in Tables 1 and 2.

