### 3. Methods

#### 3.1 Study design

This will be a prospective multi-centre open-label clinical trial at 10 pediatric centres that are members of the SIC network and the C council which is comprised of the heads of the 16 pediatric oncology and blood and marrow transplantation programs in Canada. Each participating site is run by a Site Investigator in conjunction with a nurse coordinator (SIC nurse). The coordinating site will be the Canadian Center for Vaccinology at the IWK Health Centre, Halifax, NS.

Children who were diagnosed with ALL at  $\geq 1$  year of age, are within 3-12 months of completing chemotherapy, and have not received immunizations other than influenza since completing chemotherapy will be eligible. As most centres initiate immunization at 6 months post-chemotherapy, children will be enrolled and immunized at the 6-month visit, where possible. Children can be enrolled as late as 12 months post-chemotherapy if they meet all other eligibility criteria. All participants will undergo a clinical assessment, and immunologic and serologic testing for pneumococcus, tetanus, pertussis and varicella. They will then be immunized with PCV13, DTaP-IPV-Hib, regardless of immunization history [unless PPV23 was received within the prior 12 months (see section 3.2.1)]. Other routine vaccines required as per provincial and centre-specific immunization policies will also be administered. Pneumococcal polysaccharide vaccine (PPV23) will be administered approximately 2 months after PCV13. Repeat serologic testing will be conducted at 2-3 months and 12-15 months after DTaP-IPV-Hib and PCV13 immunization to assess short and long-term immune responses.

Study visits and bloodwork will be coordinated with routine blood draws wherever possible. Baseline antibody titres will be compared to age-matched immunocompetent controls. Vaccine responses will be compared to healthy vaccine recipients in published clinical trials. Multivariable analysis will be conducted to identify predictors of low baseline antibody titres after chemotherapy and poor immune responses to vaccination.

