## **6.4 Statistical Methods**

**Immune responses:** Immune markers (see 5.2) will be compared to age-specific reference values. Baseline GMTs with 95% confidence intervals and proportion with protective titres at baseline will be reported for cases and controls, stratified by interval since last vaccination. Varicella titers will be compared pre-chemotherapy (i.e., at diagnosis) and post-chemotherapy and the proportion with loss of immunity will be reported. The proportion of subjects with GMT ratios  $\geq 4$  or protective titres at 2 and 12-15 months post-vaccination will be reported for pneumococcal vaccines (PCV13+PPV23) and DTaP-IPV-Hib, stratified by age, ALL treatment protocol (COG versus DFCI), interval from last chemotherapy to immunization, and ALL risk category. Vaccine responses will be compared to the expected responses in healthy children based on published clinical trials. Differences among categorical variables will be assessed by Pearson's  $\chi^2$  test or with Fisher exact test when expected cell sizes are  $< 5$ . Independent predictors of low baseline GMTs to tetanus toxoid and pneumococcal serotypes and of an adequate immune response to PCV13+PPV23 vaccination and DTaP-IPV-Hib booster will be assessed using multivariable regression models.

**Safety assessment:** The frequency of low impact, moderate impact and high impact or serious AEFI will be reported by vaccine type, age and ALL risk category, and compared to the published frequencies in healthy children. The frequency of events deemed to be related to vaccination based on the causality algorithm will also be reported.

All statistical analyses will be conducted using SAS® version 9.4 (Cary, NC).

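### COG versus DFCI is fixed by the treating centre, but the planned tests and the >75% power treat children as independent, which raises the false-positive rate and overstates power if centres differ

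*Combined protocol and SAP*

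**What the plan says.** Section 1.1.1 reports that most Canadian paediatric oncology centres use COG protocols and that "Three centres use the protocols developed by the Dana-Farber Cancer Institute (DFCI) ALL Consortium". Section 3.1 describes a "prospective multi-centre open-label clinical trial at 10 pediatric centres". Section 6.2 says "We expect to recruit 75–80 children over the enrollment period" and sets a quota by type of centre: "at least 30 subjects will be recruited from centres using DCFI protocols, with the remainder recruited from COG centres" (DCFI is evidently DFCI). The stated purpose of the quota is "To ensure adequate power (>75%) to assess differences in vaccine responses according to treatment protocol". No effect size, endpoint or design effect accompanies that figure.

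Section 6.4 reports vaccine responses "stratified by age, ALL treatment protocol (COG versus DFCI), interval from last chemotherapy to immunization, and ALL risk category". It tests differences in categorical variables by Pearson chi-square or Fisher exact test, and assesses predictors with multivariable regression of unspecified type. Section 6.3.2 lists treatment protocol, province, vaccine products received and type of vaccine provider as independent variables. It does not list centre. Clustering, an ICC and a centre effect are not mentioned anywhere. Section 7.4 says that the study site is entered in the database as a code.

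**The concern.** A child's protocol follows from where the child was treated, so the contrast compares a handful of centres with another handful. Children at one centre share local practice and, to some extent, population and vaccine product. If responses vary between centres for such reasons, 30 children from three centres carry less information about protocol than 30 unrelated children. The chi-square and Fisher tests ignore this, and so does a power figure computed from numbers of children.

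This is the only comparison within the cases that has its own recruitment quota and power claim. Section 1.5 says the results are to support immunization recommendations. A difference between centres reported as an effect of chemotherapy regimen could mislead that work.

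**Working it through.** **Inputs.** From the documents: 75–80 cases, at least 30 of them from DFCI centres, hence 45–50 from COG centres (6.2); 10 sites (3.1); three DFCI centres in Canada (1.1.1). Assumed: all three DFCI centres take part, so 3 against 7; an ICC from 0 to 0.20; a 60% response in both groups for the chi-square simulation. The significance level is not stated. Two-sided 5% is inferred because it reproduces a neighbouring figure, as shown next.

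**The plan's own figures.** With power = Φ(d·√(n₁n₂/(n₁+n₂)) − 1.96):

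- Cases against controls, 75 v 75, d = 0.53: Φ(0.53 × 6.124 − 1.96) = Φ(1.286) = 90.1%. The plan states 90%.
- COG v DFCI: the >75% cannot be reproduced, because no effect size is given. With independent children, 30 v 45 and d = 0.62, power is Φ(0.62 × 4.243 − 1.96) = 74.9% (76.6% for 30 v 50). On the proportion scale the figure corresponds to about 30 points: 80% v 50% gives 76.6%, and 60% v 30% gives 73.9% (30 v 45).
- At the effects used for cases against controls, 30 v 45 independent children give less: 61% for 0.53 SD and 39% for 60% v 40%.

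**False-positive rate of the child-level test.** With no protocol effect and a random centre effect, the variance of the difference is inflated by

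V = w₁[1 + (m₁ − 1)·ICC] + w₂[1 + (m₂ − 1)·ICC],

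where m = Σm²/Σm within each group, and w₁ = (1/30)/(1/30 + 1/45) = 0.6, w₂ = 0.4. The true error is 2[1 − Φ(1.96/√V)].

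- Equal centres (3 × 10 v four of 6 and three of 7): m₁ = 10, m₂ = 291/45 = 6.47, so V = 1 + 7.59·ICC.
- Uneven centres (16, 9, 5 v 12, 9, 8, 6, 5, 3, 2): m₁ = 362/30 = 12.07, m₂ = 363/45 = 8.07, so V = 1 + 9.47·ICC.

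Example: equal centres at ICC 0.05 give V = 1.379, 1.96/√1.379 = 1.669, error 9.5%. Simulation of the chi-square test on beta-binomial data agrees closely:

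| ICC | Equal: formula | Equal: simulated | Uneven: formula | Uneven: simulated |
|---|---|---|---|---|
| 0 | 5.0% | 5% | 5.0% | 5% |
| 0.01 | 5.9% | 6% | 6.1% | 6% |
| 0.02 | 6.8% | 7% | 7.2% | 7.5% |
| 0.05 | 9.5% | 10% | 10.6% | 11% |
| 0.10 | 13.9% | 15% | 16.0% | 17% |
| 0.20 | 21.7% | 23% | 24.9% | 27% |

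With only two DFCI centres (2 × 15 v 8 COG centres) the simulated error is about 12% at ICC 0.05 and 18% at 0.10.

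**Power.** Take d = 0.63 SD, where 30 v 45 independent children give 76%, and equal centres. Allowing for V but keeping the normal critical value, power is Φ(0.63 × 4.243/√V − 1.96). The last column is a t-test on the ten centre means (8 df).

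| ICC | Allowing for V | Centre means, 8 df |
|---|---|---|
| 0 | 76% | 65% |
| 0.01 | 73% | 62% |
| 0.05 | 62% | 52% |
| 0.10 | 52% | 43% |

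**The case against.** A reader might infer that centre differences will be declared protocol effects two to three times as often as 5%. The documents do not support that. The multiple needs an ICC of about 0.05–0.10, and no ICC is given. At 0.01–0.02 the error is only 6–7%. Several design features favour a low value. Each antibody is measured in one laboratory (4.3.2). Study vaccines and visits are common to all sites (3.1, Table 3). PCV13 is a single product (4.6). Province, vaccine product and type of provider are listed covariates (6.3.2). Against that, two DTaP-IPV-Hib products are permitted (4.6), and other routine vaccines follow provincial and centre policy (3.1). The direction stands; the size is conditional.

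Three further limits also stand:

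- The regression type is unspecified, so independence is certain only for the chi-square and Fisher tests. For the models it is an inference from silence.
- Section 1.1.1 counts DFCI centres in Canada, not among the ten sites, so 3 v 7 is an assumption. Fewer DFCI centres would make matters worse.
- The contrast is neither an objective (section 2) nor a named outcome (6.3.1). The quota and power claim in 6.2 still imply a test.

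The inflation is an average property. In a single data set, centre effects may cancel.

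The remedies have limits as well. The centre-means t-test loses power even at ICC 0 (65% v 76% above) and does not readily adjust for age or risk category, so it should not be the default. With ten centres the between-centre variance is poorly estimated: in simulation with equal centres, a moment estimate is zero or negative in about 45% of runs at ICC 0.02 and 33% at 0.05. A mixed model may then fall back towards the child-level analysis.

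**Conclusion.** The concern holds in conditional form. By the plan's own recruitment rule, protocol is a property of the centre, and neither the named tests nor the >75% power allows for that. Any positive between-centre variance makes the child-level test reject too often under no protocol effect, and makes the power at any given effect size lower than a calculation with independent children suggests.

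The size rests on an ICC that must be assumed, on the 3 v 7 split and on a two-sided 5% level. Over ICC 0.01–0.10 the error is about 6–15% with equal centres and 6–17% with uneven ones. It would be wrong to say either that a particular multiple of 5% will occur or that the regression models certainly ignore centre. No variance method removes the confounding of regimen with centre. The comparison of cases with controls is not affected in this way.

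**What to change.** **Section 6.4.** Analyse COG v DFCI with site as the cluster, by a random centre effect or GEE, with small-sample degrees of freedom or a bias-corrected variance, adjusted for age and risk category. Add a comparison of centre means as a sensitivity analysis. Do not use fixed centre effects in any model that contains protocol, because they are aliased with it. Show results by centre. Describe the contrast as DFCI centres against COG centres, and state that regimen and centre effects cannot be separated.

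**Section 6.2.** Replace the >75% with a figure that states its effect size and assumed ICC under that analysis, or withdraw it and call the contrast descriptive. State how many DFCI centres are among the ten sites.

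**Cost.** A few sentences and standard procedures in the SAS release already named. Site is already coded, so no extra children or data are needed. The price is a wider interval and a lower stated power for this contrast.
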